3.3.4 Pharmacokinetic Outcome Measures

The primary PK outcome measures for this study are as follows:

- PK parameters for MHAA4549A in serum including total exposure (i.e., AUC), maximum observed concentration (C_{max}), clearance, half-life, and volume of distribution, when appropriate, as data allow

The exploratory PK outcome measures for this study are as follows:

- | [REDACTED]
- | [REDACTED]

3.3.5 Exploratory Outcome Measures

The exploratory outcome measures for this study are as follows:

- | [REDACTED]
 - | [REDACTED]
 - | [REDACTED]
 - | [REDACTED]
 - | [REDACTED]
- | [REDACTED]
- | [REDACTED]
 - | [REDACTED]
- | [REDACTED]
 - | [REDACTED]
- | [REDACTED]
 - | [REDACTED]
- | [REDACTED]
- | [REDACTED]
 - | [REDACTED]
- | [REDACTED]
- | [REDACTED]
 - | [REDACTED]
- | [REDACTED]
- | [REDACTED]
 - | [REDACTED]
- | [REDACTED]
- | [REDACTED]
 - | [REDACTED]
- | [REDACTED]
- | [REDACTED]
 - | [REDACTED]
- | [REDACTED]

4. MATERIALS AND METHODS

4.1 PATIENTS

This study aims to enroll approximately 330 men and women and is designed to assess the safety and clinical activity of a single IV administration of 3600 mg MHAA4549A or a single IV administration of 8400 mg MHAA4549A in adult patients hospitalized with severe influenza A.

4.1.1 Inclusion Criteria

Patients must meet the following criteria for study entry:

- Hospitalized men or women ≥ 18 years of age on the day of signing the informed consent or obtaining surrogate consent from an authorized representative
- Diagnosis of influenza A where a Sponsor-approved influenza test is used as an aid in diagnosis. A Sponsor-approved influenza test includes:
 - Influenza antigen test –OR–
 - Influenza PCR test
- One of the following markers of severity within 24 hours of hospital admission:
 - Requirement for PPV –OR–
 - Requirement for O₂ supplementation to maintain SpO₂ > 92% (*Source documentation should show that the patient's SpO₂ was less than 92% off oxygen. Source documentation may consist of either a SpO₂ off oxygen with a value below 92% or a documentation of the Investigator's rationale in lieu of this SpO₂ documentation.*)
- A negative urine or serum pregnancy test for women of child-bearing potential
- Patients of reproductive potential must agree to use reliable means of contraception as described below as a minimum (adherence to more stringent local requirements may be required):
 - For women who are not postmenopausal (postmenopausal defined as ≥ 12 months of non-therapy-induced amenorrhea) or surgically sterile (absence of ovaries and/or uterus): agreement to remain abstinent or use two adequate methods of contraception, including at least one method with a failure rate of < 1% per year, during the treatment period and for at least 120 days after the dose of study drug

Abstinence is only acceptable if it is in line with the preferred and usual lifestyle of the patient. Periodic abstinence (e.g., calendar, ovulation, symptothermal, or postovulation methods) and withdrawal are not acceptable methods of contraception.

Barrier methods must always be supplemented with the use of a spermicide.

Examples of contraceptive methods with a failure rate of < 1% per year include tubal ligation, male sterilization, hormonal implants, proper use of combined oral or injected hormonal contraceptives, and certain intrauterine devices.

Male partners who have had a vasectomy should have the appropriate post-vasectomy documentation available of the absence of sperm in the ejaculate. The vasectomized male partner should be the sole partner for that patient.

- For men: agreement to remain abstinent or use a condom during the treatment period and for at least 30 days after the dose of study drug and agreement to refrain from donating sperm during this same period

Men with a pregnant partner must agree to remain abstinent or use a condom for the duration of the pregnancy.

Abstinence is only acceptable if it is in line with the preferred and usual lifestyle of the patient. Periodic abstinence (e.g., calendar, ovulation, symptothermal, or postovulation methods) and withdrawal are not acceptable methods of contraception.

- Non-reproductive potential is defined below (but could be superseded by local definitions, if they are more stringent):

Women who are postmenopausal (≥ 12 months of non-therapy-induced amenorrhea)

Women who are surgically sterile (i.e., hysterectomy, complete bilateral oophorectomy)

Men who are surgically sterile (i.e., castration)

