3. STUDY DESIGN

3.1 DESCRIPTION OF STUDY

3.1.1 Overview of Study Design

This is a Phase 2b (GV29216), randomized, double-blind, placebo-controlled study designed to assess the safety and clinical activity of a single IV dose of 3600 mg MHAA4549A or a single IV dose of 8400 mg MHAA4549A in hospitalized patients with severe influenza A in combination with oseltamivir versus a comparator arm of placebo with oseltamivir. *A Sponsor-approved influenza test that includes influenza antigen test or influenza polymerase chain reaction (PCR) test must be used to diagnose influenza A infection for study eligibility.* This study is planned to take place in approximately 170 study centers globally.

Initially, GV29216 targeted enrollment into two treatment groups: a single IV dose of 3600 mg of MHAA4549A with oseltamivir or a single IV dose of placebo with oseltamivir.

[figure not shown]
In this version of the protocol, patients will be randomized 1:1:1 into three treatment groups: a single IV dose of 3600 mg of MHAA4549A with oseltamivir, a single IV dose of 8400 mg of MHAA4549A with oseltamivir, or a single IV dose of placebo with oseltamivir. *Patients will be stratified by country, PPV versus supplemental O₂ at randomization, and suspected or confirmed bacterial pneumonia versus no bacterial*

pneumonia based on the status at randomization. All patients must begin study drug infusion within 48 hours of hospital admission. In addition, all patients will receive oseltamivir as standard therapy for a minimum of 5 days (10 doses) starting no later than 12 hours after completion of study drug administration. Oseltamivir treatment for longer than 5 days is permitted based on local investigator discretion.

Hospitalized patients with an O₂ or PPV requirement will be evaluated for influenza A infection. Enrollment in this study requires ongoing treatment within 24 hours of hospital admission with one of the following:

- any PPV or
- any supplemental O₂ to maintain oxygen saturation (SpO₂) > 92% ([Section 3.3.2](#))

Patients on PPV should not exceed *approximately* 45% of the total patients enrolled in the study.

[figure not shown]

Safety evaluations will also be provided by an IMC and SOC, as defined in the IMC and SOC agreement (see [Section 3.1.2](#)). If after review of available study data, the IMC and SOC conclude that there is a significant toxicity or worsening disease associated with MHAA4549A, they may recommend stopping further enrollment in the study.

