3.2 RATIONALE FOR STUDY DESIGN

3.2.1 Rationale for Study Design

Hospitalized influenza A infection represents a high unmet need, which, when left untreated, may progress to a more serious disease that may result in significant morbidity and mortality in otherwise healthy adults as well as in vulnerable populations.

This study is designed to estimate the improvement in outcome of a combination regimen of MHAA4549A with oseltamivir compared to a standard of care arm of placebo with oseltamivir. The study population will include hospitalized patients with influenza A requiring *ongoing* O₂ support and/or PPV support within 24 hours of hospital admission.

Study GV29216 will be a Phase 2b study involving approximately 330 patients. The sample size was determined based on an expected clinically meaningful difference of 1–2 days improvement in time to normalization of respiratory function between the control and treatment arms, assuming a 5 day median time to the time to normalization of respiratory function in the standard of care arm ([Blackwood et al. 2011](#); [Premier Inc, Charlotte, NC](#)).

This design ensures that all patients in the trial will receive the current NAI treatment, oseltamivir, as standard of care at a minimum, and will evaluate the clinical benefit of combining MHAA4549A with this standard of care regimen. Therefore, this study aims to identify a regimen that could deliver maximum benefit in this high unmet need disease, while still treating all enrolled patients with the currently accepted standard of care.

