3.3.2 Primary Efficacy Outcome Measures

The primary efficacy outcome measure for this study *is* as follows:

- Time to normalization of respiratory function defined as:
 - The time to cessation of O₂ support resulting in a stable SpO₂ ≥ 95% (see [Appendix 2](#) for details)

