4.1.2 Exclusion Criteria

Patients who meet any of the following criteria will be excluded from study entry:

- Pregnant or lactating, or intending to become pregnant during the study
 - Women who are not postmenopausal (postmenopausal defined as ≥ 12 months of non-therapy-induced amenorrhea) or surgically sterile must have a negative pregnancy test result within 2 days prior to initiation of study drug.
- Hypersensitivity to monoclonal antibodies or to any *constituents* (*sodium succinate, sucrose, polysorbate 20*) of MHAA4549A study drug
- Hypersensitivity to the active substance or to any excipients of oseltamivir
- Investigational therapy within the 30 days prior to study treatment
- Received prior therapy with any anti-influenza monoclonal antibody therapy (including MHAA4549A) *within* 8 months prior to study treatment
- Current treatment (within 7 days of dosing) with probenecid, amantadine, or rimantidine

- Patients who have taken more than a total of 6 doses (3 doses of peramivir) of anti-influenza therapy (e.g., oseltamivir, zanamivir, *laninamivir*, peramivir) in the period from onset of symptoms and prior to study treatment
- Admission >48 hours prior to study treatment
- Onset of influenza symptoms (including fever, chills, malaise, dry cough, loss of appetite, myalgias, coryza, or nausea) >5 days prior to study treatment
- Positive influenza B or influenza A+B infection within 2 weeks prior to study treatment
- High probability of mortality in the next 48 hours as determined by the investigator
- Patient requiring home or baseline oxygenation therapy
- Patient with history of chronic lung disease *with a documented* SpO₂ < 95% *off oxygen*
- Patient on a chronic dose of corticosteroids exceeding 10 mg/day of prednisone or equivalent steroid dose for a duration of greater than 14 days within 30 days of entry into study
- Creatinine clearance ≤ 10 mL/min
- Patients who received nasally administered influenza A vaccine within 7 days *prior to screening*
- Patients with the following significant immune suppression:
 - Bone marrow or solid organ transplant in the previous 12 months
 - Cancer chemotherapy in the previous 12 months
 - HIV infection with most recent CD4 < 200 cells/mL
 - Other significant immune suppression as determined by the investigator in discussion with the Sponsor Medical Monitor
- Patient on ECMO at time of randomization

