4.2 METHOD OF TREATMENT ASSIGNMENT AND BLINDING

The randomization of patients will be managed by a central Interactive Voice and Web Response System (IxRS) through use of a dynamic hierarchical algorithm which includes a random component. The treatment assignments will be unblinded to selected Sponsor personnel to facilitate ongoing monitoring of safety and tolerability, including members of the IMC and SOC.

All patients will be randomly assigned to receive 3600 mg MHAA4549A, 8400 mg MHAA4549A, or placebo at a 1:1:1 ratio stratified by country, whether patient is on PPV versus supplemental O₂ at randomization, and whether the patient has suspected or

confirmed bacterial pneumonia vs no bacterial pneumonia at randomization. Initially GV29216 randomly assigned patients to receive either 3600 mg MHAA4549A, or placebo at a 1:1 ratio. The updated randomization scheme takes into account the numbers already allocated to these two arms and strata prior to allocating to the three arm design so that by the end of the study there will be an approximate 1:1:1 allocation between the three arms.

All patients will receive oseltamivir (as described in [Table 2](#)) for a minimum of 5 days. Treatment for longer than 5 days is permitted based on local investigator discretion.

Unblinded personnel (i.e., unblinded site pharmacist or other designated, qualified unblinded study personnel) at each study site will prepare the IV infusions of study drug, as described in [Section 4.3.3](#). The Sponsor will provide masking bags and blinded study personnel will administer the study drug. The other parties who are involved in the conduct of the study (i.e., patients and blinded site personnel) will remain blinded to patient-specific treatment assignments until the final database lock after the completion of the study.

Bioanalytical laboratory personnel responsible for performing PK assays will be unblinded to patients' treatment assignments to identify appropriate PK samples to be analyzed. Samples from patients assigned to the comparator arm will not be analyzed except by request (e.g., to evaluate a possible error in study drug administration).

While PK samples must be collected from patients assigned to the comparator arm to maintain the blinding of treatment assignment, PK assay results for these patients are generally not needed for the safe conduct or proper interpretation of this trial.

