Appendix 1a Schedule of Activities (cont.)

[REDACTED]; AE=adverse event; APACHE=Acute Physiology and Chronic Health Evaluation; ATA=Anti-therapeutic antibodies; D=day; Dx=diagnostics; eCRF=electronic Case Report Form; ECG=electrocardiogram; HAI=hemagglutinin inhibition; [REDACTED]; ICU=Intensive Care Unit; IRB/IEC=Independent Review Board/Independent Ethics Committee; NAI=neuraminidase inhibitor; O₂=oxygen; PaO₂/FiO₂=partial pressure of oxygen/fraction of inspired oxygen; PCR=polymerase chain reaction; PD=pharmacodynamics; PK=pharmacokinetic; PPV=positive pressure ventilation; qPCR=quantitative Polymerase Chain Reaction; RBCs=red blood cells; SOFA=Sequential Organ Failure Assessment; SpO₂=oxygen saturation measured by pulse oximetry; WBCs=white blood cells.

- ^a Assessments to be performed irrespective of day of discharge. Assessments on discharge day will supersede assessments for matching day except for the study completion/early discontinuation visit (e.g., If a patient is discharged from the hospital on Day X, use assessments under “hospital discharge” column instead of the Day X column and record under the hospital discharge folder in the eCRF. If a patient discontinues from the study early on Day X, complete all assessments under the “early discontinuation” column and record under the early discontinuation folder in the eCRF.
- ^b Informed consent must be obtained from all patients. For patients who are unable to consent, an authorized representative may be used if allowed by local regulations and IRB/IEC policy.
- ^c Sponsor-approved influenza test using a nasopharyngeal swab in one nostril *or lower respiratory tract sample (if appropriate for the sponsor-approved local PCR test)*. A Sponsor-approved influenza test includes influenza antigen test or influenza polymerase chain reaction (PCR) test. Result must be available within the 48-hour screening window.
- ^d A urine *or serum* pregnancy test should be collected only for women considered by the investigator to be of childbearing potential, see exclusion criteria. This result must be available within 2 days prior to study treatment. If urine testing is not available at the site, blood already collected from an existing sample may be tested for pregnancy.
- ^e Confirm patient requires supplemental O₂ or PPV within 24 hours of hospital admission.

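### The oxygen or ventilation requirement is tied to the first 24 hours after admission but dosing may start at up to 48 hours, and the passages conflict on whether support must continue to randomization

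*Combined protocol and SAP*

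**What the plan says.** All references are to the Version 7 protocol.

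- **Eligibility.** Section 4.1.1 asks for "One of the following markers of severity within 24 hours of hospital admission": PPV, or oxygen needed to keep SpO₂ above 92%. The synopsis criterion has the same window. In Appendix 1a the row confirming the oxygen requirement is marked in the screening column only, and footnote e reads "Confirm patient requires supplemental O₂ or PPV within 24 hours of hospital admission".
- **Dosing window.** Section 3.1.1: "All patients must begin study drug infusion within 48 hours of hospital admission". The matching exclusion in Section 4.1.2 is "Admission >48 hours prior to study treatment".
- **Ongoing support.** Section 3.1.1: "Enrollment in this study requires ongoing treatment within 24 hours of hospital admission with one of the following". Section 3.2.1 describes a population needing ongoing O₂ "support and/or PPV support within 24 hours of hospital admission".
- **Stratification.** Section 4.2: "stratified by country, whether patient is on PPV versus supplemental O₂ at randomization". There are two respiratory levels and no third.
- **Primary endpoint.** Section 3.3.2: "The time to cessation of O₂ support resulting in a stable SpO₂ ≥ 95" per cent. Appendix 2 times the event at the first discontinuation of oxygen with its reading.
- **Efficacy population.** Section 6 takes randomized patients with influenza A confirmed by central PCR on Day 1 samples, with no condition on oxygen status.

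**The concern.** The eligibility test looks back to the first day in hospital, whereas stratification and the endpoint look at the patient as randomized. Up to a day or more can pass between the two, and neither 4.1.1 nor 4.1.2 requires oxygen or PPV at randomization. The protocol does use that time point elsewhere: being on ECMO at randomization is an exclusion.

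A patient who has come off support in the interval has no interpretable time to cessation of oxygen measured from randomization or dosing. If counted as an event at time zero, that patient adds an event which treatment cannot influence and pulls the estimate toward no difference. The study's stated purpose in Section 6.1 is to estimate the effect size on this endpoint, so dilution damages its main product.

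**Working it through.** **1. One patient followed through the text.** Suppose oxygen is needed at hour 4, weaned at hour 30, and the patient is randomized at hour 44.

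| Provision | Result |
|---|---|
| 4.1.1 severity marker | Met at hour 4 |
| 4.1.2 admission limit | 44 h is under 48 h, so not excluded |
| Appendix 1a, footnote e | Met at screening; no Day 1 repeat |
| 3.1.1 and 3.2.1, ongoing support | Depends on whether *ongoing* means at enrollment or within the first 24 h |
| 4.2 respiratory stratum | No level applies |
| Endpoint, SpO₂ stable at 96% on room air | Oxygen stopped 44 − 30 = 14 h before randomization |
| Endpoint, SpO₂ 93% on room air | Not met; the Appendix 2 daily trial covers patients on low-flow oxygen, so no event time is generated |
| Section 6 efficacy population | Included if the central PCR is positive |

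The protocol text in Sections 3.3.2, 6.4 and Appendix 2 gives neither a time origin for the endpoint nor a rule for a patient off support at baseline.

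**2. The plan's own power figure.** Inputs from Section 6.1 and Table 7: 330 evaluable patients, exponential times, control median 5 days, both active medians 4 days, 60 days of follow-up, two-sided α = 0.20. The stated power is 71.4%. I pooled the active arms (220 versus 110), took about 330 events, and used z = 1.282.

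- Freedman, allocation ratio φ = 2, hazard ratio θ = 5/4 = 1.25: Φ(√(φD)·|1 − θ|/(1 + φθ) − z) = Φ(√660 × 0.25/3.5 − 1.282) = Φ(0.553) = 71.0%.
- Schoenfeld, p = 1/3: Φ(√(D·p(1 − p))·|ln 0.8| − z) = Φ(8.563 × 0.2231 − 1.282) = Φ(0.629) = 73.5%.
- Simulated log-rank, 5,000 runs: 72.9%.

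The first column of Table 7 is therefore reproduced closely by a pooled log-rank comparison. Nothing in this point contradicts it.

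**3. Sensitivity to patients already off support.** Let f be their share. The documents give no value, so 5% and 10% are assumptions. All such patients are taken to have SpO₂ at or above 95% and to be spread evenly across arms.

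Medians, counting them as events at time zero: solve (1 − f)·2^(−t/m) = 0.5, which gives t = m·log₂(2(1 − f)).

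- f = 5%: log₂(1.9) = 0.926; medians 4.63 and 3.70 days; difference 0.93 day.
- f = 10%: log₂(1.8) = 0.848; medians 4.24 and 3.39 days; difference 0.85 day.

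Power:

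| f | Time-zero events (simulated log-rank) | Left out of the analysis (Schoenfeld, D = 330(1 − f)) |
|---|---|---|
| 0 | 72.9% | 73.5% |
| 5% | 69.45% | 71.9% |
| 10% | 66.4% | 70.2% |

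The rows with f above zero use 4,000 runs; the Monte Carlo standard error is about √(0.7 × 0.3/4,000) = 0.7 percentage point. The log-rank is unstratified.

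**The case against.** **The word *ongoing*.** A reader might infer that the protocol plainly permits the hour-44 patient. It does not. Section 3.1.1 makes ongoing treatment a condition of enrollment. In Section 3.2.1 the word is italicized and is absent from the Version 5 text of that section, so the sponsor appears to have been tightening the wording. Support begun within 24 hours and still running is a fair reading. This stands: the fault is a conflict between passages, not clear permission. It does not remove the fault, because 4.1.1, the synopsis criterion and footnote e, against which sites screen, lack the word.

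**Stratification as a gate.** A reader might infer that such patients must be put in a wrong stratum. That is not shown. The IxRS may refuse a patient on neither form of support, and its specification is not in the documents.

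**Endpoint already met.** A reader might infer that anyone off oxygen has reached the endpoint before dosing. That holds only if SpO₂ is also stable at 95% or above, whereas the qualifying threshold is 92%. Below 95% the event time is undefined.

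**Deliberate choice.** Section 3.2.2 justifies the population by the need for oxygen or ventilation on the first day of admission, and patients weaned early still inform safety, viral load, mortality and clinical status. This is a real reason for the 24-hour marker. It does not explain a stratification factor with no place for these patients.

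**Separate SAP and study purpose.** Section 6 defers detail to a separate SAP, which may hold a handling rule, and Section 6 plans no formal testing. Both points lower the severity. Neither settles who is eligible.

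**Conclusion.** The conflict is real and should be reconciled. As written, 4.1.1 can admit a patient off support at randomization, whose primary event is at time zero or undefined and who belongs to neither respiratory stratum.

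The size is unknown. At assumed shares of 5% and 10%, the loss is about 3 to 7 points of power and 0.07 to 0.15 day of a 1-day difference, under the exponential model, pooled active arms and time-zero counting. Leaving these patients out costs less power.

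A reader might infer a patient count by running the 5-day median from qualification: a one-day gap gives 1 − 2^(−1/5) = 12.9%, or about 43 of 330. The documents do not support that. They do not apply the 5-day median from qualification or admission, and they do not say when patients qualify, when they are dosed, or whether sites would enroll someone already weaned.

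This is an inexpensive improvement to a hypothesis-generating study, not a correction to a stated figure.

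**What to change.** Reconcile 4.1.1, 3.1.1, 3.2.1, the synopsis and footnote e of Appendix 1a so that eligibility requires the patient still to be receiving supplemental O₂ or PPV at randomization, in line with the stratification wording in 4.2. Confirm it with the Day 1 respiratory assessment, which Appendix 1a already schedules and which its general note places before study drug.

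In the analysis plan, state the time origin of the primary endpoint and how any patient randomized off support is analyzed, separately for SpO₂ at or above 95% and below it.

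The cost is amendment wording, an eligibility check at randomization, and some additional screen failures. The secondary and safety data of the patients screened out would be lost.
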